May 30, 2023

Effect of Flaxseed as a Treatment for Adults With Type 2 Diabetes Mellitus in Mexico

-CEI-04/2023-

**Study Protocol and Informed
Consent Form**

UNDER THE LEADERSHIP OF: DR. [name]

University of the Southern Sierra

University of the Southern Sierra

Effect of flaxseed consumption as a treatment for adults with type 2 Diabetes Mellitus in Oaxaca de Juarez, Oaxaca.

I. PRESENTATION OF THE PROTOCOL OR RESEARCH PROJECT

1. Summary of the study

Introduction: Type 2 Diabetes Mellitus represents one of the most important health emergencies of this century. It is estimated that by 2045 there will be 700 million people living with diabetes. Flaxseed is a food that is characterized by its nutritional properties, highlighting its content of alpha linoleic acid, flax lignans, digluc- secoisolariciresinol cosides. The latter have antioxidant, hypolipidemic and hypoglycemic effects, which makes it an excellent option as a functional treatment for type 2 diabetes.

Material and Method: Randomized clinical trial. The sample will be recruited by self-selection.

The control group will be given a nutritional education talk using the healthy eating plate and the group intervention you will be prescribed flaxseed supplementation (16 gr of flaxseed/day for three months) and also a talk of nutritional education using the healthy eating plate. A clinical history will be applied for the variables age, gender, occupation and marital status, duration of the disease, type of current diabetes treatment, control and comorbidities, weight, height and biochemical parameters glucose, glycosylated hemoglobin, total cholesterol, triglycerides, LDL cholesterol, and HDL cholesterol of each participant, at the beginning and at the end of the study.

Scientific/Practical Relevance: The use of flaxseed as a functional food for the treatment of type 2 diabetes is It has been used in different populations with success. However, in the state of Oaxaca its effectiveness has not been tested despite having this food available. If the results are positive, this food can be offered as a therapeutic alternative instead of or in combination with its pharmacological treatment, improving the results. This is important because the prevalence of this disease in the state is increasing.

Keywords: Type 2 Diabetes Mellitus, treatment, functional food, Flaxseed.

Expected start and completion dates of the study.

Start: October 2023

Study completion: March 2025

2. Objectives

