General

- To assess the adjuvant effects of flaxseed consumption (16 g of flaxseed per day/3 months) on

Biochemical factors (glucose, glycosylated hemoglobin, total cholesterol, triglycerides, LDL cholesterol and cholesterolHDL) of adult patients (30 to 70 years) with type 2 diabetes mellitus, who attend the Nutrition outpatient clinic from the Regional Hospital of Oaxaca.

Specific Objectives

1. Describe the sociodemographic variables (age, sex, occupation, marital status) of adult patients (30 to 70 years) who suffer from type 2 diabetes, who attend the Nutrition outpatient clinic at the Regional Hospital from Oaxaca.
2. Describe the clinical characteristics (time of evolution of the disease, type of treatment, control and comor-bilities), of adult patients (30 to 70 years) who suffer from type 2 diabetes, who attend the outpatient clinic of Nutrition at the Regional Hospital of Oaxaca.
3. Assess the anthropometric variables (weight and height) of adult patients (30 to 70 years) who suffer from diabetes type 2, who attend the Nutrition outpatient clinic at the Regional Hospital in Oaxaca.
4. Evaluate the biochemical parameters (glucose, glycosylated hemoglobin, total cholesterol, triglycerides, LDL cholesterol and HDL cholesterol) of adult patients (30 to 70 years) suffering from type 2 diabetes, who attend the Nutrition outpatient clinic of the Regional Hospital of Oaxaca, prior to the consumption of flaxseed and three months after regular consumption of flaxseed.

5. Apply a nutritional intervention to two groups: Group A) Teaching the healthy eating plate and Group B) Teaching healthy eating dishes and indicating flaxseed consumption.
6. Evaluate the effect of flaxseed consumption on biochemical markers (glucose, glycosylated hemoglobin, Total cholesterol, triglycerides, LDL cholesterol and HDL cholesterol of adult patients (30 to 70 years) suffering from type 2 diabetes, who attend the Nutrition outpatient clinic at the Regional Hospital in Oaxaca.
7. Analyze the most effective possible combinations (pharmacological + non-pharmacological) for the treatment of Adult patients (30 to 70 years) who suffer from type 2 diabetes, who attend the Nutrition outpatient clinic at the Regional Hospital of Oaxaca.

4. Justification

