The nutritionist will take the participant's weight and height and record them at the beginning and end of the study.

Specialized nurses will take 5 milliliters of blood in the clinical laboratory area of the Regional Hospital

from the of Oaxaca and a clinical chemist professional will assess the biochemical parameters glucose, hemoglobin glycosylated, total cholesterol, triglycerides, LDL cholesterol and HDL cholesterol of each participant, at the beginning and at the end of the study (after three months of intervention, consuming 16 g of flaxseed/day).

The effect of flaxseed consumption on biochemical markers (glucose, hemoglobin) will subsequently be evaluated.

glycosylated, total cholesterol, triglycerides, LDL cholesterol and HDL cholesterol and the possible combinations will be analyzed (pharmacological + non-pharmacological) most effective for the treatment of type 2 diabetes.

6. Selection criteria and description of participants.

Selection criteria

Patients living with type 2 Diabetes Mellitus and who come with fasting blood glucose greater than 140 and hemoglobin glycosylated greater than 6.5%, who are beneficiaries who attend the Nutrition outpatient clinic of the Hospital-Regional "Presidente Benito Juárez" diagnosed at most one year ago and who agree to participate in the study, age between 45 and 65 years with regular attendance at the outpatient clinic, minimum of 3 consecutive months.

7. Methods of selection and inclusion of participants in the study.

Phase 1. Sample recruitment.

The convenience sample will be recruited by self-selection: patients who attend the nutrition outpatient clinic that meet the inclusion criteria, they will be invited to participate in the study. After giving them all information, those who wish to participate will sign the legal informed consent for participation.

Phase 2. Case randomization procedure.

Patients who sign the informed consent will be assigned a group according to the following: in the case

If you have an even number in your file, you will be part of the control group (A), and if you have an odd number, you will be part of intervention group B.

Group A.

They will be given verbal instructions to continue with the treatment established by the treating physician, and they will be provided with nutritional guidance with the help of the healthy eating plate.

Group B.

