They will be given verbal instructions to continue with the treatment established by the treating physician, they will be given nutritional guidance with the help of the healthy eating plate and they will be provided with a pamphlet with the instructions. written and photographed on how to consume flaxseed and its benefits.

Phase 3.

Administration of flaxseed

Researchers will purchase, package, and provide flaxseed powder to members of group B. Flaxseed will be delivered in packages with 16 gr of ground flaxseed each, which will be given to patients for their daily consumption (a tablespoon of 8

gr of flaxseed in the morning snack and 8 gr of flaxseed in the afternoon snack)

(late). You will be provided with brochures with images explaining how to consume it and how the glass should look when finished. Various forms of consumption of the powder will also be provided to avoid getting bored with the taste and consistency. from dust.

Phase 4.

Surveillance and monitoring.

Daily contact will be maintained with participants via WhatsApp in order to remind them to take flaxseed.

and also to find out if they have any adverse symptoms (abdominal distension, flatulence, gas, diarrhea, etc.), as well as to resolve doubts and ask if they should start taking some vitamins, minerals or medications.

Both groups will be given a 24-hour recall and a food frequency questionnaire. every 15 days. The food consumption of both groups will be analyzed according to its nutritional content (energy, macro and micronutrients) and each nutrient will be used as a nutritional variable that can influence the control of the biochemical markers.

Phase 5.

Data analysis.

Statistical analysis will be performed using the IBM SPSS Statistics program version 24, in which it will be performed descriptive statistics and for group comparisons different tests will be performed depending on the nature of the variables. The comparison between the values measured at the beginning and the values measured after 3 months in each group will be performed using the paired t test and will be

considered statistically significant when $p < 0.05$.

Inclusion criteria:

- ÿ Patients entitled to who attend the “Presidente” Regional Nutrition outpatient clinic Benito Juárez” diagnosed at most one year ago and who agree to participate in the study by signing the informed consent.
- ÿ Patients diagnosed with uncontrolled Diabetes Mellitus evidenced by biochemical markers, den-

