within a maximum of 1 month of validity, (fasting blood glucose greater than 140 and glycosylated hemoglobin greater than (6.5%).
- ÿ Patients with regular attendance at the outpatient clinic for at least 3 consecutive months.

Exclusion criteria:

- ÿ Patients diagnosed with chronic kidney disease undergoing renal function replacement therapy.
- ÿ Patients who already consume enough fiber and omega 3, as evidenced by the application of a reminder of 24 hours and a food frequency questionnaire.
- ÿ Pregnant or
breastfeeding women.
- ÿ Patients in
menopause.
- ÿ Patients with glucose disorders secondary to autoimmune diabetes, thyroid diseases or insulin-producing tumors.
- ÿ Patients with a medical history of poor drug adherence.
- ÿ Patients with adequate glycemic control evidenced by clinical laboratory tests for at least 2 months.
- ÿ Patients who cannot read or write.

ÿ Patients who do not have a means of contact for follow-up.

Elimination criteria:

ÿ Patients who do not agree to participate in the study. ÿ Data collection instrument with incomplete items.

ÿ People who voluntarily withdraw from the study at any time. ÿ If the patient has surgery during the study.

ÿ Patient who during the study begins to consume any type of supplement (vitamins, minerals, omega 3).

ÿ Patient who stops consuming flaxseed during the study.

8. Experience of the principal investigator and co-investigators in this type of research.

(maximum)

The principal investigator has participated in different research projects in the area, both as a collaborator and as principal investigator:

-Collaborating researcher. Faculty of Nutrition. Universidad Veracruzana. **“Evaluation of waist circumference in fifth period students of proposal 3 and 4 as a risk factor for developing metabolic syndrome”**. Faculty of Nutrition. Xalapa, Universidad Veracruzana, Mexico. 2010. SATISFACTORILY COMPLETED

-Collaborating researcher. Cooperation with the Coordination of the Master's Degree in Food and Nutritional Security.

“Influence of maternal nutrition on the programming of fetal adipose tissue development”. Faculty of Nutrition. Universidad Veracruzana. 2011. SATISFACTORILY COMPLETED

-Collaborating Researcher. **“Influence of physical activity on biochemical and vascular factors determining endothelial dysfunction in postmenopausal women”**. Sant Joan de Reus University Hospital, Tarragona, Spain, 2012. SATISFACTORY COMPLETED

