-Collaborating researcher. INCOS Project (Community Health Intervention), **“Effect of a community intervention in school children, considering nutritional and cognitive status”**. Ccorca District, Cusco, Peru.

NUTRISAM Research Group of the Rovira I Virgili University, Spain. 2013. Project Grant from the Rovira i Virgili University, Spain. SATISFACTORILY COMPLETED

-Principal investigator. PESA-T Project (Health Assessment Project) **“Nutritional Transition State of the city of Cuzco, Peru”**. NUTRISAM Research Group. Project Grant from the Rovira I Virgili University, Spain. March-September 2014. SATISFACTORILY COMPLETED

-Principal investigator of the project **“EMOTIONAL NUTRITIONAL STATUS IN FOOD SAFETY AND HEALTH”**

THE OAXACAN POPULATION DURING CONFINEMENT DUE TO THE SARS-COV-2 VI-RUS”, registered at the Nutrition Institute of the University of the Sierra Sur (UNSI) with folio CEI-09A / 2020. In progress

-Principal investigator of the project **“NUTRITIONAL STATUS, FOOD CONSUMPTION AND INTAKE NUTRITIONAL IN CONFIRMED AND RECOVERED CASES BY SARS-Cov-2 IN THE STATE OF OAXACA, MEXICO”**, registered at the Nutrition Institute of the University of the Sierra Sur (UNSI) with the folio INUT/NC/2021/01/270821. In progress

-Co-technical manager of the Project **“Molecular epidemiology of drug use and comorbidities in Mexican population, as well as its repercussions on the Mexican legal framework”**, registered in the Institute of Nutrition from the University of the Sierra Sur. INUT/BMBCS/05/2020. In progress

9. Potential risks and benefits for participants and for society, as well as compensation for those involved participants.

According to the general health law on health research in its article 17, this is considered Low risk study because biochemical tests will be taken and this could cause the participant pain in the extraction area, and you may also experience some symptoms from taking flaxseed such as constipation, diarrhea, or gastrointestinal upset.

The participant will not receive financial compensation, but the results of the study will be published and disseminated. Based on the results of the studies, participants may potentially receive the benefit of improved controlling your type 2 diabetes.

10. Management of potential risks for participants.

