To minimize risks, researchers will be in daily contact with participants to warn them any damage to health and to know if any gastrointestinal reaction or even allergic reaction occurs, this in order to be able to tell you what to do or even stop the study if necessary. In case the discomfort persists, the responsibility of the research team will be guaranteed to provide immediate nutritional care to the participant (as established in articles 18 and 19 of the Regulations) of the General Health Law on Health Research).

The risk management process will be as follows:

1. Identify risk	The patient will be monitored in case of any health problems caused by flaxseed.
2. Analyze	The symptom will be analyzed.
3. Prioritize risk	It will be verified that your health is not compromised.
4. Control the risk	If the symptom is controllable, the treatment will continue and if it is not, the patient can withdraw.

of the study. If the patient presents any

stress problems due to the administration
tion is withdrawn from the study.

11. Procedure by which consent to participate in the study will be obtained.

- Participants who meet the inclusion criteria will be recruited in the nutrition outpatient clinic from the Regional Hospital of Oaxaca.
- You will be provided with detailed information about the study and will be provided with written informed consent/legal participation document (ANNEX 1)
- You will be given time to proceed with the reading of the document and you will have time in case the participant has doubts or questions about the study.

12. Management of confidentiality of information.

Upon entering the study, each participant will be registered with a number by which they will be addressed throughout the study. All data will be treated anonymously.

13. Conflicts of interest.

There is no conflict of interest

14. Bibliography

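### Stopping flaxseed for any reason is an elimination criterion that only group B can meet, so one group loses participants after allocation and its 3-month change may look better than it would for everyone allocated

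*Protocol*

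**What the plan says.** The elimination criteria in section 7 of the protocol include "Patient who stops consuming flaxseed during the study". No reason, duration or exception is attached. The same list eliminates people who withdraw voluntarily, have surgery, start a supplement or have an incomplete data form. The term elimination is not defined.

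Flaxseed powder is supplied to group B only (section 7, Phase 3). Both groups continue their usual treatment and receive dietary guidance, and group A has no placebo or other product that it could stop (section 7, Phase 2).

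Section 9 warns that "you may also experience some symptoms from taking flaxseed such as constipation, diarrhea, or gastrointestinal upset". Section 7, Phase 3, offers several ways of taking the powder so that participants do not tire of it. For an uncontrolled problem, step 4 of the table in section 10 reads "If the symptom is controllable, the treatment will continue and if it is not, the patient can withdraw". That row continues: the withdrawal is from the study, and a participant with stress attributed to taking flaxseed is withdrawn, with no option stated.

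Section 5 plans the laboratory tests "of each participant, at the beginning and at the end of the study", and the same sentence describes the final test as following three months of flaxseed. The analysis is a paired t test of baseline against 3 months within each group, with unspecified further tests for group comparisons (section 7, Phase 5).

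**The concern.** The criterion acts after allocation, depends on what happens under treatment, and can be met in one group only. The other elimination criteria can arise in either group, so they do not offset it. If those who stop differ in glucose, HbA1c or lipid response from those who continue, the group B that reaches the 3-month analysis is a selected part of the group B that was allocated, while group A has undergone no matching selection. Whatever comparability allocation provided is then lost.

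The use of the result is at stake. Section 1 says that, if results are positive, "this food can be offered as a therapeutic alternative instead of or in combination with its pharmacological treatment". Patients who are offered flaxseed will include some who cannot or will not keep taking it. A result from continuers alone does not speak for them.

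**Working it through.** **Step 1: what happens to a participant who stops.** Setting sections 7 and 10 side by side gives these routes:

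- Stops for any reason: eliminated (section 7).
- Has an uncontrolled symptom: may withdraw from the study (section 10, step 4), and voluntary withdrawal is also an elimination criterion (section 7).
- Has stress attributed to taking flaxseed: is withdrawn (section 10, step 4).

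None of these routes leads to a month-3 value counted in group B. If elimination means leaving the study, the month-3 blood is not drawn. If it means leaving the data set, the value is not used.

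**Step 2: which group is affected.** Only group B receives flaxseed, so removal under this criterion falls on group B alone.

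**Step 3: possible size.** The protocol gives no sample size, symptom rate or stop rate, so there is no figure of its own to reproduce. The values below are assumptions, for illustration only.

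Let s be the share of group B that stops and is removed, C the continuers' mean 3-month change, and rC the mean change that those who stop would have shown. The mean for everyone allocated to group B is

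(1 − s)C + s·rC = C[1 − s(1 − r)],

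so the continuers' mean equals the mean for everyone allocated times 1/[1 − s(1 − r)].

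| r | s = 5% | s = 10% | s = 20% |
|---|---|---|---|
| 0 | 1/0.95 = 1.05 | 1/0.90 = 1.11 | 1/0.80 = 1.25 |
| 0.5 | 1/0.975 = 1.03 | 1/0.95 = 1.05 | 1/0.90 = 1.11 |
| 1 | 1.00 | 1.00 | 1.00 |

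If r exceeded 1, the denominator would exceed 1 and the factor would fall below 1, so group B would look worse than it should. The row r = 0 is extreme, because those who stop would still have usual treatment and dietary guidance.

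**Step 4: the same on the scale of a group difference.** Let g be how much worse the mean change is in those who stop than in continuers, in SD units. The continuers' mean then exceeds the mean for everyone allocated by s × g. Group A has no matching removal, so the difference between groups shifts by the same amount:

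- 10% × 0.5 SD = 0.05 SD
- 20% × 0.5 SD = 0.10 SD
- 30% × 1.0 SD = 0.30 SD

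The shift is zero when g = 0, and it reverses when those who stop would have done better.

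**The case against.** The strongest defence is that the trial asks about consumption, not prescription. The general objective and specific objectives 4 and 6 are worded around consuming flaxseed; objective 4 speaks of values "three months after regular consumption of flaxseed". A consumers-only result fits that wording, and this part of the defence stands. It does not cover the statement in section 1 about offering flaxseed as a therapeutic alternative. Nor does it make a selected group B comparable with an unselected group A.

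A second defence is that analysis populations belong in a statistical analysis plan, which is not shown, and that the consent annex cannot be seen. The reading of what happens to those who stop is therefore limited to the visible text. But the criterion is fixed in the protocol itself. If it ends participation, no later plan can analyse blood that was never drawn.

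Third, the daily reminders and varied ways of taking the powder should reduce stopping. That bears on how often it happens, not on the rule.

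The documents do not support some stronger readings:

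- *That the result will be biased in favour of flaxseed.* The direction is plausible but not established, and nothing is known about how many will stop or how they would respond.
- *That the criterion targets intolerance.* It names no reason; boredom with the powder counts equally.
- *That section 5 contradicts the criterion by promising a final test for every participant.* Its sentence ties that test to three months of consumption.
- *That the sponsor has decided to offer flaxseed to patients.* Section 1 states a possibility, conditional on positive results.
- *That participants with symptoms are left without care.* Daily contact is used "and also to find out if they have any adverse symptoms", and section 10 states "In case the discomfort persists, the responsibility of the research team will be guaranteed to provide immediate nutritional care to the participant".

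**Conclusion.** The point holds as a design weakness that should be corrected. A stated rule removes participants from one group after allocation for a reason tied to the treatment, and nothing visible keeps them in follow-up or in the analysis. This breaks the comparability of the groups and may make group B's 3-month change look better than it would for everyone allocated.

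Neither size nor direction can be determined from the protocol. The factors of 1.00 to 1.25 and the shifts of up to 0.30 SD rest wholly on assumed stop rates and responses, and their range includes no bias. The conclusion also assumes that elimination takes the participant out of the 3-month results. The protocol does not say so outright, but it lists elimination apart from exclusion, applies it to incomplete data forms as well, and nowhere retains those eliminated. Confidence is medium.

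**What to change.** - In section 7, delete stopping flaxseed from the elimination criteria and record it as an event, with its date and reason.
- In step 4 of section 10, allow flaxseed to be stopped, for a symptom or for stress, while the participant stays in the study.
- Take the planned month-3 blood test from these participants unless they withdraw consent for follow-up.
- Analyse all participants in their allocated group. Keep a consumers-only analysis, labelled secondary, for the objectives worded around consumption.

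The cost is protocol wording, a few extra contacts, and blood tests that were already planned. The downside is some dilution of the month-3 effect by participants who are no longer taking flaxseed. That dilution is part of what offering flaxseed to patients would achieve.

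### Section 10 foresees an allergic reaction, but its step 4 default of continuing flaxseed while a symptom is controllable makes no exception for suspected allergy

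*Protocol*

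**What the plan says.** Protocol Section 9 (potential risks and benefits) classes the study as low risk and, apart from pain at the blood draw, expects "symptoms from taking flaxseed such as constipation, diarrhea, or gastrointestinal upset".

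Section 10 (management of potential risks) looks wider. Daily contact with participants is meant, among other things, "to know if any gastrointestinal reaction or even allergic reaction occurs". The same sentence gives the purpose: to be able to "tell you what to do or even stop the study if necessary". If discomfort persists, the research team is "guaranteed to provide immediate nutritional care to the participant", with a reference to articles 18 and 19 of the health research regulations.

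A four-step table follows as the risk management process. The patient is monitored for problems caused by flaxseed (step 1), the symptom is analysed (step 2), and then "It will be verified that your health is not compromised" (step 3). Step 4 gives the action: "If the symptom is controllable, the treatment will continue and if it is not, the patient can withdraw". The same row adds a separate withdrawal rule for "stress problems due to the administration".

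Under Section 7, Phase 3, group B takes 8 g of ground flaxseed in the morning snack and 8 g in the afternoon snack. The summary and Section 5 give the duration as three months. The elimination criteria include "Patient who stops consuming flaxseed during the study".

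**The concern.** The section names two kinds of reaction and then gives the symptom one default action. For bloating or loose stools, continuing while the complaint is manageable is sensible, because what matters is how well the participant tolerates it. For a suspected allergy, how manageable the present symptom is does not settle the matter. A first reaction may be slight and easily handled, and the risk is what happens on the next exposure. The test in step 4 therefore asks the wrong question for one of the two events the section foresees.

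What is at stake is participant safety. Flaxseed is taken twice a day, so the next exposure is never far off. A participant with, say, a mild rash or itching that was judged controllable would be kept on it under the rule as written, and nothing in the text shown requires a clinician to agree.

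**Working it through.** The protocol gives no figure on this point and no arithmetic applies. The check is to follow a mild suspected allergic symptom in group B through the text and see whether anything takes it off the continue path.

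1. **Is the event foreseen?** Yes. Section 10 names an allergic reaction as something daily contact should reveal. The point therefore concerns how a stated rule fits a stated event.

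2. **What does the opening paragraph of Section 10 do with it?** It allows advice, or stopping when needed. That is a power to act. It sets no default for allergy and does not say when stopping becomes necessary.

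3. **What do steps 2 and 3 do?** The symptom is analysed and the participant's health is checked. A marked reaction should fail step 3. A mild one, such as a localised itch that settles, can reasonably pass, because health is not compromised at that moment.

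4. **What does step 4 do with a symptom that has passed?** It makes continuation the stated course if the symptom is controllable. If it is not, the participant may withdraw. The only other rule visible in that row concerns stress problems. It does not mention allergy, and because the row is broken in the text available, nothing here is built on it.

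5. **Does another section supply the exception?** Section 7, Phase 4 (surveillance and monitoring) lists digestive complaints with an open-ended ending and attaches no action to any of them. The exclusion criteria do not mention allergy. The elimination criteria have no rule for an adverse reaction. They do include stopping flaxseed, which could be read to cover a precautionary pause.

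Set side by side:

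| Symptom | Step 3 check | Step 4 as written | Suitable? |
|---|---|---|---|
| Gastrointestinal, controllable | passes | continue | yes |
| Gastrointestinal, not controllable | may fail | may withdraw | acceptable |
| Allergic, marked | should fail | should not reach the continue default | covered, by judgment |
| Allergic, mild and controllable | can pass | continue | no |

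Only the last row is a problem, and no visible text changes its outcome. The judgment in that row rests on the general clinical principle that re-exposure is the hazard in allergy. The protocol does not state that principle.

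**The case against.** The strongest reply is that step 4 should not be read alone. The one sentence that mentions allergy also mentions stopping, and step 3 comes before step 4, so continuation presupposes that health is not compromised. Participants may also withdraw voluntarily at any time under the elimination criteria. Much of this stands. It disposes of the reading that someone with a serious allergic reaction would be kept on flaxseed: the documents do not support that. It does not reach the mild case, where step 3 can be passed, the power to stop is discretionary, and the only specific instruction is to continue.

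A second reply is that articles 18 and 19, the consent form and the group B pamphlet are not shown and may contain allergy instructions. That is possible, and no claim is made that they lack them. Even so, they would leave the wording of step 4 in the protocol as it is.

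Some stronger inferences are tempting and should be resisted:

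- A reader might infer that one rule governs all symptoms. The stress provision in the same row shows otherwise.
- A reader might infer that nobody is responsible for the judgment. Section 10 places contact and responsibility with the researchers and the research team. A named individual role would be further detail, and its absence is not an error.
- A reader might infer that nutritional care is the prescribed response to allergy, or that medical care is ruled out. The guarantee is tied to persisting discomfort, most naturally gastrointestinal, and nothing shown forbids medical assessment.
- A reader might count the servings left in the three months as a measure of harm. That is only the dosing calendar, and it assumes that none of the safeguards operates.

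**Conclusion.** The concern holds in a narrow form. For a mild, controllable, suspected allergic symptom that passes the step 3 check, the protocol's written default is to continue flaxseed, with no exception for an event that the same section foresees. This is a rule that fits one of its cases badly.

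It is a minor patient-safety correction. The size of the harm cannot be given, because the documents state no allergy rate and none is assumed here. Allergy is mentioned as a contingency, the study is classed as low risk, and no efficacy estimate is directly affected. The conclusion assumes that step 4 is applied as worded, that the broken table row hides no allergy provision, and that re-exposure is the relevant hazard. Confidence is medium, mainly because of that row and the material not shown.

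**What to change.** In Section 10, step 4, limit the continue-if-controllable rule to gastrointestinal symptoms. Add a separate rule for a suspected allergic reaction: hold flaxseed at once, refer the participant to the treating physician or the hospital, and resume only if that clinician agrees.

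In the elimination criteria, add a clause that a clinician-directed hold does not by itself meet "Patient who stops consuming flaxseed during the study". Without it, a precautionary pause could be read as ending participation, which would discourage the team from ordering one.

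The cost is a few sentences in Section 10 and one clause in the elimination criteria. In practice it means a little physician time and possibly a few more discontinuations in group B. Recruitment is at a hospital clinic and participants already have treating physicians, so no new service is needed.
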